3. Baseline research leukapheresis (50-100 mL approximate total volume, for immunological monitoring) – to take place within 4 weeks prior to day 1.
NOTE: For patients unable to undergo leukapheresis at this time point, a 200-cc blood draw may be substituted (twenty 10-mL green-top heparinized tubes).
4. Tetanus immunization (to take place after baseline leukapheresis and prior to day 1)
5. 20 mL peripheral blood (red-top tubes) for sera to evaluate baseline antibody responses, and 20 mL peripheral blood (green-top tubes) for CTC baseline evaluation
6. FLT PET/CT scan (to occur within 4 weeks prior to day 1).
7. Tissue biopsy – metastatic site – to take place within 2 weeks prior to day 1

C. Immunization #1 (Day 1)

1. Physical examination, symptoms assessment, and ECOG performance score
2. Blood draw for CBC, differential and platelets, chemistry panel, PSA and PAP
3. Subjects will receive pTVG-HP DNA immunizations intradermally on the deltoid area of the lateral arm (preferentially left arm) with 0.25 mL administered at each of two adjacent sites.

4. Following vaccinations, the subjects will be observed for 60 minutes for unanticipated adverse events.
- D. ARM 1 SUBJECTS ONLY: Anti-PD-1 #1 (Day 1, 1-3 hours after day 1 immunization)
1. Pembrolizumab 2 mg/kg administered intravenously over 30 minutes
 2. Subjects will be observed for additional 30 minutes for unanticipated adverse events. Vital signs (temperature, heart rate and blood pressure) will be assessed and recorded by the staff prior to, and at the end of, the treatment period.
- E. Immunization #2 - Day 15 (+/- 3 days)
1. Subjects will receive pTVG-HP DNA immunizations intradermally on the deltoid area of the lateral arm (preferentially left arm) with 0.25 mL administered at each of two adjacent sites.
 2. Following vaccinations, the subjects will be observed for 60 minutes for unanticipated adverse events.
- F. ARM 1 SUBJECTS ONLY: Anti-PD-1 #2 - Day 22 (7 +/- 3 days after day 15 visit)
1. Physical examination, symptoms assessment, and ECOG performance score
 2. Blood draw for CBC, differential and platelets, chemistry panel, PSA and PAP
 3. Pembrolizumab 2 mg/kg administered intravenously over 30 minutes
 4. Subjects will be observed for additional 30 minutes for unanticipated adverse events. Vital signs (temperature, heart rate and blood pressure) will be assessed and recorded by the staff prior to, and at the end of, the treatment period.

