1. Subjects will receive pTVG-HP DNA immunizations intradermally on the deltoid area of the lateral arm (preferentially left arm) with 0.25 mL administered at each of two adjacent sites.
 2. Following vaccinations, the subjects will be observed for 60 minutes for unanticipated adverse events.
- M. 3-Month Follow-up - Day 85 (14 +/- 3 days after day 71 visit)
1. Physical examination, symptoms assessment, and ECOG performance score.
 2. Blood draw for CBC, chemistry panel, serum PSA and PAP (can be performed +/- 7 days of this visit)
 3. 10 ml peripheral blood (red-top tubes) for sera to evaluate antibody responses, and 100 ml peripheral blood (green-top heparinized tubes) for T-cell response evaluation and CTC analysis (can be performed +/- 7 days of this visit)
 4. CT scan of abdomen and pelvis, bone scintigraphy (can be performed +/- 7 days of this visit, but prior to pembrolizumab treatment for patients in Arm 2)
 5. FLT PET/CT scan (can be performed +/- 7 days of this visit, but prior to pembrolizumab treatment for patients in Arm 2)
 6. Tissue biopsy of same metastatic lesion as in pre-treatment period (can be performed +/- 7 days of this visit, but prior to pembrolizumab treatment for patients in Arm 2)

ARM 2 SUBJECTS ONLY – Anti-PD-1 #1:

7. Pembrolizumab 2 mg/kg administered intravenously over 30 minutes
8. Subjects will be observed for an additional 30 minutes for unanticipated adverse events. Vital signs (temperature, heart rate and blood pressure) will be assessed and recorded by the staff prior to, and at the end of, the treatment period.

N. DAY 106 – (21 +/- 3 days after day 85 visit):

1. Physical examination, symptoms assessment, and ECOG performance score.
2. Blood draw for CBC, chemistry panel, serum PSA and PAP

ARM 2 SUBJECTS ONLY – Anti-PD-1 #2:

3. Pembrolizumab 2 mg/kg administered intravenously over 30 minutes
4. Subjects will be observed for an additional 30 minutes for unanticipated adverse events. Vital signs (temperature, heart rate and blood pressure) will be assessed and recorded by the staff prior to, and at the end of, the treatment period.

O. DAY 127 – (21 +/- 3 days after day 106 visit):

1. Physical examination, symptoms assessment, and ECOG performance score.
2. Blood draw for CBC, chemistry panel, serum PSA and PAP

ARM 2 SUBJECTS ONLY – Anti-PD-1 #3:

3. Pembrolizumab 2 mg/kg administered intravenously over 30 minutes

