1. To determine whether either treatment sequence, or PAP-specific immune response, is associated with prolonged (6-month) radiographic progression-free survival
2. To evaluate effects of schedule (concurrent versus delayed administration of pembrolizumab) on the magnitude of PAP-specific T-cell responses, PD-1 expression on circulating T cells, and PD-L1 expression on circulating epithelial cells (CEC) and on tumor biopsies
3. To determine the median time to radiographic progression using concurrent administration schedules

The exploratory objectives are to:

1. To evaluate effects of treatment on the number of circulating tumor cells
2. To evaluate PAP-specific antibody responses following treatment with pembrolizumab and pTVG-HP DNA vaccine
3. To determine whether treatment with either sequence elicits immunologic antigen spread to other prostate associated antigens

4. To determine whether pre-existing or vaccine-induced PD-L1 expression on CEC or tumor biopsies is predictive of objective clinical response
5. To determine whether treatment elicits expression of other regulatory molecules on tumor-specific T cells (e.g. TIM3, BTLA, and LAG3) or tumor cells (e.g. HVEM, phosphatidyl serine, PD-L2)
6. To determine whether PD-1-regulated antigen-specific T-cells identified by *trans vivo* DTH testing can identify patients who develop objective clinical responses with PD-1 blockade therapy in combination with pTVG-HP.
7. To determine whether changes in lymph nodes and soft tissue lesions are observed by FLT PET/CT after treatment with vaccine with or without pembrolizumab
8. To determine if PD-1 inhibitor therapy in combination with pTVG-HP will change number and activity (SUV) in osteoblastic metastases as measured by NaF PET/CT.

C. Study Design

The study is designed as a randomized, two-arm, open-label, single institution pilot trial. Study arms will be defined as follows:

- Arm 1: pTVG-HP (100 µg) with rhGM-CSF (208 µg) administered intradermally (i.d.) biweekly 6 times beginning at day 1 pembrolizumab 2 mg/kg, administered intravenously every 3 weeks 4 times, beginning at day 1
- Arm 2: pTVG-HP (100 µg) with rhGM-CSF (208 µg) administered intradermally (i.d.) biweekly 6 times beginning at day 1 pembrolizumab 2 mg/kg, administered intravenously biweekly 6 times, the first dose administered two weeks after the last pTVG-HP vaccination

Eligible subjects will be randomly assigned in 1:1 fashion to either Arm 1 or Arm 2.

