The expected 6-months progression-free survival rate in Arm 2 (pembrolizumab is administered sequentially after pTVG-HP) is 25%. It is hypothesized that the treatment of pTVG-HP, when administered concurrently with pembrolizumab (Arm 1), will result in a substantial increase in the 6-month progression-free survival rate. Specifically, it is anticipated that the 6-month progression-free survival rate in Arm 1 will be at least 65-75%. The following table shows the required sample sizes for detecting various differences in the 6-month progression-free survival rates between the two study arms, assuming 80% power and a one-sided 0.10 significance level. Since this is a pilot study, a less stringent significance level of 0.10 rather the traditional 0.05 level will be used for the primary efficacy evaluation.

	6-month progression free survival rate Arm 1			
6-month progression free survival rate Arm 2	0.65	0.70	0.75	0.80
0.20	15	11	10	9
0.25	17	15	11	10

A sample size of 15 patients per arm is proposed. This sample size will provide 80% power to detect an anticipated absolute difference of at least 45% (e.g., 25% vs. 70% or 20% vs. 65%) in the 6-months progression free survival rates between the two arms. These calculations are based on Fisher’s exact test. Furthermore, the proposed sample size of 15 patients per arm is also sufficient to provide accuracy in estimating toxicity rates. Specifically, the toxicity rates (i.e., of grade ≥ 2, grade ≥ 3, grade 4 toxicities) for each arm will be estimated with a standard error of less than 15% and the 95% confidence interval of the toxicity rates will be no wider than 45%. The probability of observing at least one event of a serious adverse event within a study arm is >95% if the adverse event rate is 20%. Analogously, the probability of observing at least one event of serious adverse event is at least 79% if the adverse event rate is only 10%.

In order to account for unevaluable (for efficacy evaluation) patients, 32 eligible patients (16 per arm) will be accrued and randomized. Based on past experience with this patient population treated at our institution, we anticipate that the proposed total number of 32 patients will be accrued within 18 months.

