F.4.3. Objective Response Rate and PSA Response Rate

The objective response rate and PSA response rate will be calculated for each study arm and for both arms combined along with the corresponding 95% confidence intervals. The Wilson score method will be used to construct the confidence intervals. Fisher's exact test will be used to compare the objective response and PSA response rates between study arms. Duration of response will be analyzed using the Kaplan-Meier method.

F.5. Analysis of Secondary Endpoints

F.5.1. PAP-Specific Immune Response

The number and frequencies of PAP-specific immune responses will be summarized in tabular format for each study arm and both study arms combined. A log-linear model will be used to evaluate whether PAP-specific immune response predicts the 6-months progression-free survival rate. The interaction between treatment (pembrolizumab administered sequentially versus delayed) and PAP-specific immune response will be included in the model. Analogously, a Cox proportional hazard regression model will be used to examine the association between PAP-specific immune response and the time to radiographic progression.

F.5.2. PAP-Specific T-Cell Response, PD-1 Expression, PD-L1 Expression

PD-1 and PD-L1 expression levels will be summarized in terms of means, standard deviations and ranges for each study arm separately and for both arms combined. The number and frequencies of PAP-specific T-cell responses will be summarized in tabular format. Fisher's exact test will be used to compare the PAP-specific T-cell response rates between study arms. A linear regression model or a negative binomial regression model will be utilized to evaluate the effects of schedule (concurrent versus delayed administration of pembrolizumab) on PD-1 expression on the number of circulating T cells, and PD-L1 expression on the number of circulating epithelial cells. The

choice of the model will be dependent on the distribution of the outcome variables (number of circulating T-cells and number of circulating epithelial cells).

F.6. Exploratory Analyses

F.6.1. Evaluation of Treatment Effects on the Number of Circulating Tumor Cells

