The number of circulating tumor cells will be summarized in terms of means and standard deviations. Within each arm, and for both arms combined, changes in the number of circulating tumor cells from the pre-treatment (date of screening/randomization) to the post-treatment assessments (day 43, day 85, day 169, month 9, and off-study) assessments will be evaluated using a paired t-test. A two-sample t-test will be used to compare the number of circulating tumor cells at each time point, and the changes in the number of circulating tumor cells from the pre-treatment assessment, between study arms. In order to evaluate longitudinal changes in the number of circulating tumor cells, linear mixed effects modeling with subject specific random effects will be conducted.

F.6.2. Evaluating of Treatment Effects on PAP-specific Antibody Responses

The number and frequency of PAP-specific antibody responses will be summarized in tabular format, stratified by study arm and for both arms combined. A generalized linear mixed effects model with subject specific random effects will be used to evaluate the treatment effect of the proposed pTVG-HP DNA vaccine and pembrolizumab (sequentially versus concurrently) combination on PAP-specific antibody response.

F.6.3. Evaluation whether Treatment with either Sequence Elicits Immunologic Antigen Spread to other Prostate Associated Antigens

The detection of antigen spread to other prostate associated antigens, and the identification of specific antigens recognized, will be analyzed descriptively. Furthermore, linear regression analysis will be conducted to evaluate whether treatment with either sequence (pembrolizumab administered sequentially or concurrently) elicits immunologic antigen spread to other prostate associated antigens.

F.6.4. Evaluation of Pre-Existing or Vaccine Induced PD-L1 Expression on CEC or Tumor Biopsies as a Predictor for Clinical Response

Logistic regression analysis will be conducted to examine whether pre-existing or vaccine induced PD-L1 expression on CEC or tumor biopsies predict clinical response. This analysis will be conducted for both arms combined. The results will be summarized in terms of odds ratios along with the corresponding 95% confidence intervals.

F.6.5. Evaluation whether Treatment with either Sequence Elicits other Regulatory Molecules on Tumor-Specific T cells or Tumor Cells

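### F.6.4 states no arm term for its pooled PD-L1 regression, although on-treatment PD-L1 is measured after different treatment in the two arms

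*Combined protocol and SAP*

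**What the plan says.** Section 11.F.6.4 gives the method in one sentence: "Logistic regression analysis will be conducted to examine whether pre-existing or vaccine induced PD-L1 expression on CEC or tumor biopsies predict clinical response". It then adds "This analysis will be conducted for both arms combined", and asks for odds ratios with 95% confidence intervals. It mentions no arm covariate, stratum or interaction, and no other section supplies one for this analysis.

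Other parts of the plan bear on it:

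- F.5.1, the model for PAP-specific immune response and 6-month progression-free survival, does bring treatment in: "The interaction between treatment (pembrolizumab administered sequentially versus delayed) and PAP-specific immune response will be included in the model".
- Secondary objective 2 asks about the effect of schedule on, among other things, "PD-L1 expression on circulating epithelial cells (CEC) and on tumor biopsies".
- Section 9.M allows the day 85 biopsy within 7 days of the visit, "but prior to pembrolizumab treatment for patients in Arm 2". Arm 1 has pembrolizumab scheduled on days 1, 22, 43 and 64.
- F.4.3 compares objective and PSA response rates between arms.
- F.1 sets a two-sided 0.05 level by default and promises a detailed SAP before the final analysis.

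**The concern.** Post-baseline PD-L1 does not follow the same treatment in the two arms. At the day 85 biopsy it reflects vaccine plus four scheduled doses of PD-1 blockade in Arm 1, and vaccine alone in Arm 2. Section 9.M does not state the same ordering for the day 85 blood draw used for circulating cells. Even so, with a 7-day window Arm 2 could have had at most one dose by then.

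If the schedule also changes the chance of response, PD-L1 in a pooled model acts partly as a label for arm. It can then look predictive although it separates responders from non-responders in neither arm. If the PD-L1 shift runs against the response difference, a real association can be hidden. At stake is whether a reported odds ratio says anything about individual patients or only restates the schedule they received.

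**Working it through.** **Inputs.** From the plan: 15 evaluable patients per arm (11.E), two-sided 0.05 (F.1), and an intended minimum of 6 biopsy pairs per arm (Section 9). Response rates and PD-L1 shifts are not in the plan. Those below are assumptions.

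**The plan's own figure.** F.6.4 states none. The 15 per arm in 11.E reproduces: with a one-sided Fisher's exact test at 0.10, the smallest n with at least 80% power is 15, both for 25% v 70% (power 0.823) and for 20% v 65% (power 0.827).

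**Mechanism.** Take equal arms, response rates p1 and p2, mean PD-L1 higher by d SD in Arm 1, and no link between PD-L1 and response within either arm. Pooled, responders and non-responders then differ in mean PD-L1 by

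d × [p1/(p1 + p2) − (1 − p1)/(2 − p1 − p2)].

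- 30% v 10%: d × (0.30/0.40 − 0.70/1.60) = 0.31d
- 40% v 10%: d × (0.40/0.50 − 0.60/1.50) = 0.40d
- 50% v 10%: d × (0.50/0.60 − 0.50/1.40) = 0.48d
- 25% v 25%: d × (0.25/0.50 − 0.75/1.50) = 0

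The spurious difference vanishes if d = 0 or p1 = p2, so both arm effects are needed.

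**False-positive rate, 15 per arm.** Simulation: PD-L1 normal with SD 1 and mean shifted by d in one arm, response depending on arm only, likelihood-ratio test for PD-L1 at 0.05.

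| Response rates | Pooled, no arm term, d = 1 to 1.5 |
|---|---|
| 20% v 10% | about 7-9% |
| 30% v 10% | about 11-15% |
| 40% v 10% | about 17-21% |
| 50% v 10% | about 23-34% |

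Separate runs agree to within two or three percentage points (40% v 10%: 16-22% and 15-23%; 50% v 10%: 21-33%). With an ordinary arm term the rate is about 7-9%. With arm in a Firth-penalised model it is about 4-5%.

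**When one arm effect is absent (16 per arm).** With 25% v 25% response, the pooled test rejects in 5.6-6.1% of trials for d from 0 to 1.5. With 70% v 25% and d = 0 it rejects in 6.8%, against 7.2% with an arm term. The excess over 5% is the small-sample behaviour of the likelihood-ratio test, not confounding.

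**Size of the bias (16 per arm, 30% v 10%).** The median pooled odds ratio per SD, where the true within-arm value is 1, is 1.03, 1.16, 1.28 and 1.40 for d = 0, 0.5, 1 and 1.5.

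**Masking.** With a true within-arm log odds ratio of 1.2 per SD, 50% v 10% response and a 1 SD shift in the opposite direction, the pooled model detects the association in 15% of trials and the arm-adjusted model in 69%.

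**Biopsy subset, 6 per arm.** At 40% v 10% the expected number of responders is 6 × 0.40 + 6 × 0.10 = 3.0. The chance that the 10% arm has none is 0.9^6 = 0.53. In data this sparse, an ordinary likelihood-ratio test with an arm term rejects in 13-16% of trials with no association, and the Firth version in 1-3%.

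**The case against.** The strongest reply is that F.6.4 names the dataset, not the covariates. Pooling the arms does not forbid an arm term, Section 11.F is an outline, and a detailed SAP is promised. That stands as far as it goes: the accurate statement is that no arm term is stated, not that the plan excludes one. But F.5.1 does specify treatment in its model, so a SAP author following F.6.4 as written would have no reason to add it.

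A reader might infer that the plan itself expects both shifts. The documents do not support that. Secondary objective 2 asks whether schedule affects PD-L1 and gives no direction or size. The gain that 11.E predicts for Arm 1 ("will result in a substantial increase in the 6-month progression-free survival rate") concerns progression-free survival, whereas exploratory objective 4 concerns objective response, for which no arm difference is planned. The introduction reports no objective responses among 25 prostate cancer patients on PD-1 blockade alone, so small response differences are plausible. At 20% v 10% the pooled test is barely worse than the adjusted one.

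There is also partial protection. F.5.2 summarises PD-L1 by arm and F.4.3 reports response by arm, so a careful reader can see whether both conditions hold. That flags the problem but does not correct the odds ratio. For biopsies, sparse data are a larger problem than the missing arm term; that objection also stands.

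**Conclusion.** The point holds in a conditional form. Followed as written, F.6.4 yields a pooled odds ratio for post-baseline PD-L1 that is biased if arm affects both PD-L1 and response. A reader might go further and conclude that pooling will produce a false predictor. It will not necessarily do so: the inflation ranges from almost nothing to about a third of trials, depending on arm effects that the plan does not quantify, and it disappears if either is absent.

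Nor does the concern reach pre-existing PD-L1. That is measured before treatment in randomized arms, so arm is not a systematic confounder there. Extending it to F.6.6 would need separate working and is not claimed.

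This is an exploratory analysis in a pilot with no multiplicity adjustment, and no decision rule depends on it. The consequence is limited to how the biomarker result is read.

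**What to change.** In F.6.4, for post-baseline PD-L1 only, include randomized arm as a covariate or stratum in a Firth-penalised or exact logistic regression, and report the arm-adjusted odds ratio with its 95% CI. Leave the baseline PD-L1 analysis unchanged. For the biopsy subset, use the same penalised or exact fit, show PD-L1 and response by arm, and label the result descriptive.

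The change is a line or two of SAP wording. The cost is one extra parameter with few responders, hence wider intervals, most noticeably for biopsies, where one arm may contribute no information. For the full arms the loss is small: with no arm differences, 30% response and a within-arm log odds ratio of 1.2 per SD, power was 79% pooled and 78% with an arm term.
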